5.1.1 Sotuba/Bamako Pilot Study

The open-label, dose-escalating pilot study is designed to evaluate vaccine safety and reactogenicity in healthy Mali adults living in a low malaria transmission setting (Sotuba, a suburb of Bamako, Mali). Subjects enrolled in the initial safety cohort will receive a single dose of a single antigen (either Pfs25M or Pfs230D1M) prior to vaccinating new enrolled subjects who will receive the co-administration of Pfs25M and Pfs230D1M. Additional subjects (n=10 per arm; Arms 1b, 2b, 3b, 4a, 4b) will be enrolled to receive the targeted vaccine dose for further safety and immunogenicity evaluation as outlined in **Appendix A**. Data from subjects enrolled in Arms 1b, 2b, 3b, 4a, and 4b will additionally contribute to functional activity via SMFA analyses

and will be used for exploratory objectives examining the antibody repertoire of functional antibody responses to vaccination. No blinding will be implemented, but comparators will be enrolled to control for variable natural blocking activity that may present during the rainy season and as safety controls. Randomization will occur in Arms 1b, 2b, 3b, 4a, 4b. Arms 1a, 2a, 3a will enroll in the study on an available basis.

5.1.2 Bancoumana and Doneguebougou Main Study

The double-blind, randomized, comparator controlled portion of the study is designed to also evaluate study vaccine safety and reactogenicity in healthy malaria-exposed individuals, but is powered as well to assess for immunogenicity and functional activity via SMFA and DSF.

Following scheduled, intentional unblinding at study day 336, subjects from the main study will be offered re-enrollment into the open label fourth vaccination.

5.2 Study Endpoints

5.2.1 Primary Endpoint

- Incidence of local and systemic AEs and SAEs in Malian adults. (All arms)
- Incidence of local and systemic AEs and SAEs in Malian adults. (Arms 2c, 2d, 4c)

5.2.2 Secondary Endpoints

- Anti-Pfs25 IgG levels as measured by ELISA. (All arms)
- Anti-Pfs230 IgG levels as measured by ELISA. (All arms)
- TRA/TBA of induced antibody in SMFA. (All arms except 1a, 2a, 3a)
- Transmission interruption activity measured by DSF. (Arms 2c, 2d, 4c only)

5.2.3 Exploratory Endpoints

- Cellular immune responses to vaccination. (All arms except 1a, 2a, 3a)
- Whole genome transcriptional profiling. (All arms except 1a, 2a, 3a)
- Antibody levels against recombinant EPA, and other malaria antigens, such as Pfs48/45, expressed during the gametocyte development. (All arms except 1a, 2a, 3a)
- Schistosomiasis detection (in urine). (Arms 2c, 2d, 4c only)
- qPCR for helminth detection (from stool). (Arms 2c, 2d, 4c only)
- Sequence B cell receptor/antibody genes. (All arms except 1a, 2a, 3a)

5.3 Sample Size and Estimated Duration of Study

A total of 305 subjects will be vaccinated in this trial. Note: more subjects may be initially enrolled, receive drug treatment (Coartem[®]) prior to vaccination, but no more than 305 subjects

will receive at least one vaccine. Each subject will be monitored actively for at least 6 months after the last vaccination, for a total of 12 to 16 months, depending on the vaccination schedule and timing of screening for the study. Up to 900 subjects will be screened to accommodate possible screening failures.

Participants who had previously been enrolled in the study (up to 301) will be re-enrolled for an additional 6 to 18 months depending on arm assignment and timing of reconsent.

Definitions for the purpose of this study:

- Screened – subjects will receive a study identification number when the informed consent is signed and will either be determined as “enrolled” or “screen failures” as noted below.
 - Screening may be completed over the course of multiple visits.
 - Screening, in most cases, will occur within 56 days prior to enrollment into the study
 - If the screening visit is >56 days prior to enrollment, then an updated medical review, physical exam/vital signs, repeat Malaria Comprehension Exam, and repeat laboratory evaluation (inclusive of safety labs, HIV, Hepatitis B, C) will be completed to determine eligibility for enrollment.
- Enrolled – subject will be considered enrolled beginning with the receipt of the first vaccination or at time completion of randomization.
- Randomized – the subjects are considered randomized when they meet the following criteria:
 - Confirmation that the inclusion/exclusion criteria are met.
 - Randomization number assigned. Note, randomization number may be the same as the study identification number.
- Screen Failures – subjects are considered screen failures when they meet 1 of the following criteria after signing consent:
 - Screening results reveal that the subject is ineligible per **Section 6.4** and/or **6.5**.
 - Subject withdraws consent before being vaccinated and/or randomized
- Discontinued – subject are considered discontinued when they meet 1 or more of the following criteria:
 - Subject withdraws consent after being vaccinated and/or randomized.
 - Subject is withdrawn by the PI/Sponsor after being vaccinated and /or randomized.

- Completed -- subjects are considered completed when they complete the final study visit for their arm.
- Re-enrolled – subject will be considered re-enrolled beginning with signing of the re-enrollment consent form.

6 Study Population

6.1 Description of Population and Sites

6.1.1 Rationale for Research Subject Selection

Healthy volunteers will be recruited for this study.

6.2 Clinical Sites

The study will be carried out in collaboration between the LMIV/NIAID/NIH and the MRTC in Bamako, Mali. The study will be conducted by the MRTC at three locations in Mali, West Africa (see **Map 1**). The MRTC staffing at the Mali site is employed by NIAID/USTTB programs and assigned to the Sotuba/Bamako, Bancoumana, and Doneguebougou sites for the duration of the study to provide clinical care and execute the protocol.

Map 1: Map Showing the Three Study Sites

6.2.1.1 Sotuba/Bamako Site

Bamako is the capital of Mali, located on the Niger river and has a population of about 1.7 million people. The district of Bamako is divided into urban (hypoendemic) and periurban (mesoendemic) areas and peripheral villages (hyperendemic). Sotuba is a village located on the outskirts of Bamako on the bank of the Niger River, consisting of ~6,500 inhabitants. Malaria transmission follows the same seasonality as in Bancoumana and Donéguébougou, although entomological inoculation rates are historically much lower. The annual rainfall varies between 800 mm and 1000 mm and occurs from June to October. Many clinical trials (malaria vaccine and drug trials), as well as epidemiological and entomologic malaria studies, have been done in Sotuba. As in Donéguébougou and Bancoumana, the MRTC maintains a medical clinic and laboratory in Sotuba and has been working at this site since 1993.

To note, if any issues arise prohibiting starting the study within Bamako and/or Sotuba, this phase of the study (as outlined in [Appendix A](#)) can be completed in either Bancoumana or Doneguebougou.

6.2.1.2 Bancoumana and Doneguebougou Site

Bancoumana is located 60 kilometers southwest of Bamako and has a population of about 9,000 people. The site is situated in the south-Sudanian area of Mali. The climate is hot, with daily temperatures ranging from 19°C to 40°C. The annual rainfall varies between 600 mm and 1200 mm and occurs from June to October. Many clinical trials, as well as epidemiological and entomologic malaria studies, have been done in Bancoumana.²⁶⁻²⁸

Doneguebougou is a community located 30 km north of Bamako and has a population of about 2,000, with another 2,000 inhabitants in the surrounding villages. For the purpose of vaccine trials, adequate facilities for conducting an interventional trial have been put in place at Doneguebougou within walking distance to the residents' homes. At Doneguebougou, the malaria transmission is highly seasonal, with the transmission season taking place from June until December. Doneguebougou is situated in a high transmission area, with entomological inoculation rates (determined by human landing catch) as high as 137 to 167 infectious bites per person over 1 transmission season.

Healthy adult subjects will be recruited from the surrounding community and villages, and the demographics of the study population will therefore be representative of that community.

6.3 Recruitment

Community permission will be obtained from village elders and other community members in Sotuba/Bamako, Bancoumana, and Doneguebougou after explanation and discussion of the study at a community meeting (see [Section 15.2.1](#)). A general announcement inviting household and

family members to the participating clinic to learn about the study will be made at the time of community permission, using local radio or any traditional channel of communication.

6.4 Inclusion Criteria (Initial enrollment and Re-enrollment)

All of the following criteria must be fulfilled for a volunteer to participate in this trial:

1. Age ≥ 18 and ≤ 50 years. (*Note for re-enrollment: ≤ 52 years*)
2. Available for the duration of the trial.
3. Able to provide proof of identity to the satisfaction of the study clinician completing the enrollment process.
4. In good general health and without clinically significant medical history in the opinion of the investigator.
5. Females of childbearing potential must be willing to use reliable contraception (as defined below) from 21 days prior to Study Day 0 (Study Day 476 for re-enrollment) and then until 3 months after last vaccination. (*Arms 2c, 2d, 4c only for re-enrollment*)
 - Reliable methods of birth control include **one** of the following: confirmed pharmacologic contraceptives (parenteral) delivery; intrauterine or implantable device.
 - Reliable methods of birth control include concurrent use of a pharmacologic and a barrier method, i.e. **two** of the following: confirmed pharmacologic contraceptives (oral, transdermal) delivery or vaginal ring **AND** condoms with spermicide or diaphragm with spermicide.
 - Non-childbearing women will also be required to report date of last menstrual period, history of surgical sterility (i.e. tubal ligation, hysterectomy) or premature ovarian insufficiency (POI), and will have a baseline urine or serum pregnancy test performed.
6. Willingness to have blood samples stored for future research.
7. Willingness to undergo DSFs (*Arms 2c, 2d, 4c only*).
8. Known resident of Bancoumana or Doneguebougou or surrounding area or known student or long term resident (more than 1 year) of Bamako/Sotuba, Mali

6.5 Exclusion Criteria (Initial enrollment and Re-enrollment)

A subject will be excluded from participating in this trial if any one of the following criteria is fulfilled:

1. Pregnancy as determined by a positive urine or serum human choriogonadotropin (β -hCG) test (*if female*). (*Arms 2c, 2d, 4c only for re-enrollment*)

NOTE: Pregnancy is also a criteria for discontinuation of any further dosing or non-safety related interventions for that subject.
2. Currently breast-feeding (*if female*). (*Arms 2c, 2d, 4c only for re-enrollment*)

3. Behavioral, cognitive, or psychiatric disease that in the opinion of the investigator affects the ability of the participant to understand and comply with the study protocol.
4. Hemoglobin, WBC, absolute neutrophils, and platelets outside the local laboratory-defined limits of normal (subjects may be included at the investigator's discretion for 'not clinically significant' values outside of normal range and \leq Grade 1). (*Arms 2c, 2d, 4c only for re-enrollment*)
5. Alanine transaminase (ALT) or creatinine (Cr) level above the local laboratory-defined upper limit of normal (subjects may be included at the investigator's discretion for 'not clinically significant' values outside of normal range and \leq Grade 1). (*Arms 2c, 2d, 4c only for re-enrollment*)
6. Infected with human immunodeficiency virus (HIV), hepatitis C virus (HCV), or hepatitis B (HBV). (*Arms 2c, 2d, 4c only for re-enrollment*)
7. Evidence of clinically significant neurologic, cardiac, pulmonary, hepatic, endocrine, rheumatologic, autoimmune, hematological, oncologic, or renal disease by history, physical examination, and/or laboratory studies including urinalysis.
8. History of receiving any investigational product within the past 30 days.
9. Participation or planned participation in a clinical trial with an investigational product prior to completion of the follow up visit 28 days following last vaccination OR planned participation in an investigational vaccine study until the last required protocol visit
10. Subject has had medical, occupational, or family problems as a result of alcohol or illicit drug use during the past 12 months.
11. History of a severe allergic reaction or anaphylaxis. (*Arms 2c, 2d, 4c only for re-enrollment*)
12. Severe asthma, defined as asthma that is unstable or required emergent care, urgent care, hospitalization, or intubation during the past 2 years, or that has required the use of oral or parenteral corticosteroids at any time during the past 2 years. (*Arms 2c, 2d, 4c only for re-enrollment*)
13. Pre-existing autoimmune or antibody-mediated diseases including but not limited to: systemic lupus erythematosus, rheumatoid arthritis, multiple sclerosis, Sjögren's syndrome, or autoimmune thrombocytopenia. (*Arms 2c, 2d, 4c only for re-enrollment*)
14. Known immunodeficiency syndrome. (*Arms 2c, 2d, 4c only for re-enrollment*)
15. Known asplenia or functional asplenia. (*Arms 2c, 2d, 4c only for re-enrollment*)
16. Use of chronic (≥ 14 days) oral or intravenous corticosteroids (excluding topical or nasal) at immunosuppressive doses (i.e., prednisone > 10 mg/day) or immunosuppressive drugs within 30 days of Study Day 0. (*Arms 2c, 2d, 4c only for re-enrollment*)
17. Prior to Study Day 0 and every subsequent vaccination day, receipt of a live vaccine within the past 4 weeks or a killed vaccine within the past 2 weeks. (*Arms 2c, 2d, 4c only for re-enrollment*)

18. Receipt of immunoglobulins and/or blood products within the past 6 months. (*Arms 2c, 2d, 4c only for re-enrollment*)
19. Previous receipt of an investigational malaria vaccine in the last 5 years. (For re-enrollment – does NOT include receipt of Pfs230D1M-EPA/AS01) (*Arms 2c, 2d, 4c only for re-enrollment*)
20. History of severe reaction to mosquito bites (*Arms 2c, 2d, 4c only*)
21. History of allergy to the comparator vaccine (*Initial enrollment: such as latex, yeast, or previous Hepatitis B vaccine*) (*Re-enrollment: Arm 4c only; previous meningococcal vaccine components, diphtheria toxoid or CRM₁₉₇ containing vaccine*)
22. History of Guillain-Barre syndrome (*Re-enrollment: Arm 4c only*)
23. Known allergies or contraindications (such as significant cardiac disease; prolonged QTc >450 ms; currently taking medications that may prolong your QTc; serious side effects from Coartem[®] in the past) to study treatment (Coartem[®] [artemether/lumefantrine]) (*Arms 2c, 2d, 4c only*) (*Initial enrollment only*)
24. Other condition that in the opinion of the investigator would jeopardize the safety or rights of a participant participating in the trial, interfere with the evaluation of the study objectives, or would render the subject unable to comply with the protocol.

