7.6 Prohibited Medications and Procedures

Treatment with any of the following medications/procedures could potentially interfere with vaccine-induced immunity and will not be permitted. Use of any of these during the study may exclude a subject from receiving further doses of the study vaccine. However, the subject will be encouraged to remain in the study for safety evaluations.

- Licensed killed vaccines in the two week period prior to and following each vaccination or licensed live vaccines in the four week period prior to and following each vaccination.
- Receipt of immunoglobulins and/or any blood products up to 6 months prior to the first vaccination and for 30 days after administration of the last dose of vaccine.
- Chronic oral or intravenous administration (≥ 30 days) of immunosuppressive doses of steroids, i.e., prednisone >10 mg per day, immunosuppressants, or other immune-modifying drugs from each day of vaccination to 2 weeks following each vaccination.
- Any investigational drug or investigational vaccine other than the study vaccine during the study period.
- Required surgical removal of the spleen or the development of a hematologic or other disease that would interfere with normal immunity.

Over-the-counter medications, such as acetaminophen or ibuprofen, may be used to help relieve symptoms from vaccination and are not considered prohibited.

Use of antimalarial medications or antibiotics that have antimalarial activity administered during the study period is not exclusionary, but will be documented by clinical staff and will be taken into consideration during data analysis.

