8.1.2 Rescreening for Re-enrollment (2018)

The purpose of the re-screening visit is to determine subject eligibility for continued study participation. Screening procedures include the informed consent process, laboratory assessments (for Arm 2c, 2d, 4c only on study day 364) and clinical assessments. Rescreening activities can occur over multiple visits if necessary, including the day of re-enrollment.

For Arms 2c, 2d, 4c, in the event that a chronic illness and/or HIV, HBV, or HCV is discovered during the course of rescreening, long-term treatment and care will not be reimbursed by the study, but referral for continuing care can be provided to subjects.

Per national requirements for reporting communicable diseases, confirmed positive test results for HIV, HBV, and HCV will be reported to the local health department according to applicable laws and appropriate medical referrals initiated.

The following screening evaluations must be completed for all subjects upon re-enrollment into the study:

- Explain the study and informed consent document to the subject.
- Ensure the subject has acknowledged consent by signing or fingerprinting the informed consent document. Ensure that the subject receives a signed copy of the informed consent.
- Elicit a complete medical history, including menstrual and contraceptive history and/or history of surgical sterility for females, and medication use.

- Females of childbearing potential must be willing to use reliable contraception from at least 21 days prior to first vaccination through three months after the last vaccination. *(not required for re-enrollment of the pilot study)*
- Administer a complete physical examination, including vital signs (height, weight, blood pressure, temperature, and heart rate).
- HIV pre- and post-test counseling as indicated including follow-up contact with subject to report the results and referral for appropriate medical care if indicated. *(not required for re-enrollment of the pilot study)*
- Obtain approximately 10 mL of blood for complete blood count (CBC) with differential and platelet count, ALT, creatinine (Cr), hepatitis B surface antigen, hepatitis C antibody, and HIV antibody. *(not required for re-enrollment of the pilot study)*
- Obtain urine (or serum) for pregnancy testing (for females) and urinalysis/urine dipstick for protein and blood. *(not required for re-enrollment of the pilot study)*

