Note, for re-enrollment, rescreening procedures will be completed >56 days prior to vaccination #4 as subjects enrolled in this study in Arms 2c, 2d, 4c have already been screened for HIV, Hep B, Hep C prior as well as had clinical labs monitored on multiple occasions over the course of their study participation in the last year. Given the background rate of these diseases in the community, the likelihood of a new infection with HIV, Hep B, Hep C is low. In addition repeat clinical labs will be completed prior to vaccination #4 and those with clinically significant findings will not be vaccinated or will have their vaccination delayed.

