3. Record AEs and concomitant medications, if applicable.
4. Obtain approximately 7 mL of blood for malaria blood smear, malaria PCR, SMFA, and anti-Pfs230 antibody ELISA.

Study Day 308 (±21 days; 140 days after Vaccination #3)

1. Perform basic history and focused physical examination, emphasizing examination of any acute complaints.
2. Record vital signs (blood pressure, temperature, and heart rate).
3. Record AEs and concomitant medications, if applicable.
4. Obtain approximately 1 mL of blood for malaria blood smear and malaria PCR.

Study Day 336 (±21 days; 168 days after Vaccination #3)

1. Perform basic history and focused physical examination, emphasizing examination of any acute complaints.

2. Record vital signs (blood pressure, temperature, and heart rate).
3. Record AEs and concomitant medications, if applicable.
4. Obtain approximately 47 mL of blood for malaria blood smear, malaria PCR, SMFA, and anti-Pfs230 antibody ELISA, and cellular assays, *ex vivo* assays, B cell assays and transcriptional analysis.
5. Scheduled unblinding of all subjects
 - a. Offer ENGERIX-B (or other approved Hepatitis B vaccine) to those subjects that received TBV(s) during the study.

Re-enrollment visits

Study Day 462 +/-70 days (294 days after Vaccination #3); Re-screening

1. Explain the study and informed consent document to the subject.
2. Ensure the subject has acknowledged consent by signing or fingerprinting the informed consent document. Ensure that the subject receives a signed copy of the informed consent.
3. Elicit a complete medical history, including menstrual and contraceptive history and/or history of surgical sterility for females, and medication use.
4. Females of childbearing potential must be willing to use reliable contraception from at least 21 days prior to fourth vaccination through three months after the fourth vaccination.
5. Administer a complete physical examination, including vital signs (height, weight, blood pressure, temperature, and heart rate).
6. HIV pre- and post-test counseling as indicated including follow-up contact with subject to report the results and referral for appropriate medical care if indicated.
7. Obtain approximately 16 mL of blood for complete blood count (CBC) with differential and platelet count, ALT, creatinine (Cr), hepatitis B surface antigen, hepatitis C antibody, HIV antibody, malaria blood smear, malaria PCR, SMFA, and anti-Pfs230 antibody ELISA.

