8. Obtain urine (or serum) for pregnancy testing (for females) and urinalysis/urine dipstick for protein and blood.

Study Day 476 ±56 days (308 days after Vaccination #3; Day of Vaccination #4)

The following evaluations/procedures will be completed before vaccination:

1. Verify that informed consent was obtained.
2. Ensure that all inclusion/exclusion criteria are met.
3. Ensure that CBC, ALT, creatinine, HIV/HCV/HBV, and urine results from re-screening are within protocol-defined limits (see Exclusion Criteria above) before vaccinating.
4. Perform interim history and physical examination, focusing on any acute complaints.
5. Record vital signs (blood pressure, temperature, and heart rate).
6. During the physical examination, study staff will educate the subject regarding signs and symptoms of potential adverse events (AEs) and indications for use of antipyretics if fever, headache, or malaise occurs.
7. For females, obtain a urine or serum sample for β -hCG testing. Ensure that the test is negative before vaccinating; a positive test will exclude the subject from the trial.
8. For females, ensure agreement and compliance with pregnancy prevention before vaccinating.

9. Obtain approximately 32 mL of blood for malaria blood smear, malaria PCR, SMFA, and anti-Pfs230 antibody ELISA, and cellular assays, *ex vivo* assays, B cell assays and transcriptional analysis.
10. Confirm that all criteria for vaccination have been met according to inclusion/exclusion criteria, including reviewing safety labs prior to vaccination.
11. Confirm continued eligibility to receive vaccination
12. Administer the vaccine.

The following evaluations/procedures will be completed following vaccination:

1. Observe the subject for at least 30 minutes after vaccination to evaluate immediate adverse reactions.
2. Record vital signs (blood pressure, temperature, and heart rate).
3. Perform interim history and physical examination, focusing on any acute complaints.
4. Record AEs and concomitant medications, if applicable.

Study Day 477 \pm 0 days (1 day after Vaccination #4)

1. Perform basic history and focused physical examination (including injection site), emphasizing examination of any acute complaints.
2. Record vital signs (blood pressure, temperature, and heart rate).
3. Record AEs and concomitant medications, if applicable.

Study Day 479 \pm 1 day (3 days after Vaccination #4)

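### Exclusion 16 is applied again at re-enrolment in Arms 2c, 2d and 4c, but its 30-day look-back still counts from Study Day 0, about 15.6 months before dose 4

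*Combined protocol and SAP*

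**What the plan says.** Section 6.5 is one list of exclusions for both initial enrolment and re-enrolment. Item 16 excludes people on oral or intravenous steroids for 14 days or more at immunosuppressive doses, "or immunosuppressive drugs within 30 days of Study Day 0". Its tag says that at re-enrolment it applies to Arms 2c, 2d and 4c. Section 8.1.1 identifies Study Day 0 as the day of first vaccination.

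Appendix C puts vaccination #4 on Study Day 476 with a window of 56 days either side. Among the steps before that vaccination is "Ensure that all inclusion/exclusion criteria are met".

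Section 7.6 separately lists treatments that "could potentially interfere with vaccine-induced immunity and will not be permitted". For steroids it sets a duration of at least 30 days, and it restricts these, immunosuppressants and other "immune-modifying drugs from each day of vaccination to 2 weeks following each vaccination". Use of a listed treatment may, not must, bar further doses.

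**The concern.** The re-enrolment tag has a purpose only if item 16 is meant to screen the weeks before dose 4. The wording does not do that: it asks again about the month before dose 1, for which these people were already cleared.

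Neighbouring criteria were adapted. Inclusion 5 in section 6.4 gives Study Day 476 as the reference day for re-enrolment, and exclusion 17 extends its vaccine look-back to each later vaccination day. That points to an anchor left unedited, not to a deliberate choice.

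At stake is the response to dose 4. Staff who apply the text as written would not screen out, before the booster, drug use that the plan thought worth excluding before dose 1. Section 7.6 gives the reason itself: possible interference with vaccine-induced immunity.

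**Working it through.** **Timing.** Inputs: vaccination #3 on Day 168, and vaccination #4 stated as 308 days later with a 56-day window (Appendix C).

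- The plan's figure reproduces: 168 + 308 = 476.
- Distance from the anchor in item 16: 476 / 30.4375 = 15.64 months.
- Earliest dose 4: 476 - 56 = Day 420, and 420 / 30.4375 = 13.8 months.
- Latest dose 4: 476 + 56 = Day 532, and 532 / 30.4375 = 17.5 months.
- Period that item 16 covers as written: Day -30 to Day 0.
- Period that matters for a dose on Day 476: 476 - 30 = 446, so Day 446 to Day 475. The two do not overlap.

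**Is item 16 the odd one out?** Seven exclusions carry a dated look-back: 8, 10, 12, 16, 17, 18 and 19. Items 8, 10, 12, 18 and 19 run back from the time of asking (past or last). Item 17 names Study Day 0 and every later vaccination day. Only item 16 is fixed to Study Day 0 alone.

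**What section 7.6 already catches.** Its window after dose 3 ends on 168 + 14 = Day 182, and the next opens on Day 476. It has no look-back before the dose for these drugs. But a steroid course of 30 days or more cannot fit inside a 14-day window, so the rule must reach courses already under way on the dose day. The 30-day qualifier is taken here to apply to the steroids only.

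| Drug use before dose 4 | Item 16 as written | Section 7.6 | Item 16 re-anchored |
|---|---|---|---|
| Immunosuppressant still in use on the dose day | not caught | caught | caught |
| Steroid course of 30 days or more, still in use on the dose day | not caught | caught | caught |
| Immunosuppressant stopped within the 30 days before | not caught | not caught | caught |
| Steroid course of 14 days or more, stopped within the 30 days before | not caught | not caught | caught |
| Steroid course of 14 to 29 days, still in use on the dose day | not caught | not caught | caught |

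The last three rows are the gap.

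**Other cover.** Medication use is elicited at rescreening (section 8.1.2 and Appendix C). An interim history precedes dose 4 (Appendix C), and Appendix B schedules concomitant-medication review at the vaccination #4 visits. Exclusions 7, 12, 13 and 24, deferral under section 7.4.1.2 and the last bullet of section 7.6 may also stop a dose. These either collect information or rest on disease or judgement. None is a dated rule on these drugs for dose 4. The instruction "Record AEs and concomitant medications, if applicable" comes after the injection on that day's list.

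**The case against.** The strongest reply is that nobody would read item 16 literally. Its tag makes sense only if dose 4 is meant, the criteria are checked again on the dose day, and staff will have taken a history. Most of this stands. It shows that the fault is in the drafting, and it is why the point is minor. It does not remove the fault: an eligibility rule should state the period it screens, and this one states a different period.

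Three stronger readings are tempting, and the documents do not support them.

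- *The rescreening dates widen the gap.* They do disagree: "rescreening procedures will be completed >56 days prior to vaccination #4" and "laboratory assessments (for Arm 2c, 2d, 4c only on study day 364" in section 8.1.2, against "Study Day 462 +/-70 days (294 days after Vaccination #3); Re-screening" in Appendix C. But because Appendix C repeats the criteria check on the day of dose 4, the rescreening date does not decide what a correctly anchored item 16 would cover. That disagreement is a separate matter.
- *The whole 30 days before dose 4 are unprotected for everyone.* Section 7.6 reaches immunosuppressants and long steroid courses still in use on the dose day, so only the last three rows of the table are left.
- *The direct skin feed comparison loses a stated amount of its planned 80% effect (section 14.5).* Any such figure needs a count of affected people, and the documents give no rate of use. It would also need complete non-response in people with up to three earlier doses. Section 3.5.2.2 reports both vaccine arms above control on ELISA and SMFA 12 weeks after dose 3 (p<0.0001), and any blunting would bear on what dose 4 adds.

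**Conclusion.** Item 16 is wrong as written, and the error is minor. At re-enrolment it screens a period that ended about 15.6 months before dose 4 (13.8 to 17.5 months across the window). After section 7.6 is taken into account, no dated rule covers immunosuppressants or immunosuppressive-dose steroids stopped within the 30 days before dose 4, or steroid courses of 14 to 29 days.

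The effect is probably very small, on the assumption that such drug use is rare in healthy adults. It cannot be sized from the documents. It touches the immune response to dose 4 and the secondary endpoints built on it. A reader might also infer a safety risk, but no section shows one, and the primary safety objective is not affected. No sample size or power figure changes.

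**What to change.** In item 16, replace the anchor with: *within 30 days of Study Day 0 (for re-enrollment: within 30 days of the actual day of vaccination #4, nominally Study Day 476)*.

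The word *actual* matters because of the 56-day window. A look-back fixed to Day 476 would cover Days 446 to 475. That lies wholly after a dose given on Day 420, and it ends 532 - 475 = 57 days before a dose given on Day 532.

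The cost is one clause. Medication use is already asked about at rescreening and medication review is already scheduled around vaccination #4, so no new visit or test is needed. The downside is that a rare dose 4 may have to be deferred within its window or withheld.
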